Health status (EQ-5D-5L, including Visual Analogue Scale [VAS]) will be assessed via a comparison of EQ-5D-5L health status change scores from baseline to follow-up between treatment arms. In addition, responder analyses will be conducted 1) for those who improve and 2) for those who deteriorate, utilizing the CIDs for health status VAS scores for both treatment arms.

Data Monitoring/Other committee: Yes

A Data Monitoring Committee (DMC) has been appointed for this study. The Data Monitoring Committee (board) is a group of independent scientists who are appointed to monitor the safety and scientific integrity of a human research intervention, and to make recommendations to the Sponsor regarding the stopping of a study for harms. The composition of the committee is dependent upon the scientific skills and knowledge required for monitoring the particular study. The data monitoring committee specific roles and interaction with the Sponsor will be described in the DMC charter.

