Secondary	
Key Secondary
 
• Demonstrate the efficacy non-inferiority between isatuximab SC and isatuximab IV in combination with Pd.• Demonstrate the PK non-inferiority between isatuximab SC and isatuximab IV in combination with Pd.• Assess safety of isatuximab SC and IV in combination with Pd.• Assess patient satisfaction with isatuximab SC and IV. 
Other Secondary
 
• Assess efficacy of isatuximab SC compared to isatuximab IV in combination with Pd.	
• Very Good Partial Response or better rate: defined as the proportion of participants with sCR, CR, and VGPR according to the 2016 International Myeloma Working Group (IMWG) criteria assessed by IRC.• Observed concentration before dosing (C_{trough}) at 4 weeks (ie, CT4W corresponding to predose at C2D1).• Incidence rate of infusion-reactions (IRs).• Percentage of participants satisfied or very satisfied with the injection method used to administer study medication based on the patient experience and satisfaction questionnaire (PESQ).• Duration of response (DOR): defined as the time from the date of the first response to the date of first occurrence of progressive disease (PD) as determined by IRC or death from any cause, whichever happens first. DOR is determined only for participants who have achieved a response (PR or better). In the absence of PD or death before the analysis cut-off date, the DOR will be censored at the date of the last valid disease assessment performed prior to initiation of a further anti-myeloma treatment or the analysis cut-off date, whichever is earlier. Patients with two or more consecutive missed assessments prior to PD or death will be censored at the last valid disease assessment. Details about censoring rule will be provided in statistical analysis plan (SAP).• Time to first response (TT1R): defined as the time from randomization to the date of first IRC determined response (PR or better) that is subsequently confirmed. Details about censoring rule will be provided in SAP.

Objectives	Endpoints

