
Assess safety of isatuximab SC and IV and local tolerability of isatuximab SC in combination with Pd.Characterize PK of isatuximab SC and IV in combination with Pd.Assess the delivery performance of the (investigational) device injector.Assess the potential immunogenicity of isatuximab SC and IV in combination with Pd.	
Time to best response (TTBR): defined as the time from randomization to the date of first occurrence of IRC determined best overall response (PR or better) that is subsequently confirmed. Details about censoring rule will be provided in SAP.Progression free survival (PFS): defined as the time from the date of randomization to the date of first documentation of PD as determined by IRC or the date of death from any cause, whichever comes first. Responses will be determined according to IMWG criteria. Progression based on paraprotein will be confirmed based on two consecutive assessments. PFS will be censored at the date of the last valid disease assessment not showing disease progression performed prior to initiation of a further anti-myeloma treatment (if any) or the analysis cut-off date, whichever comes first. Patients with two or more consecutive missed assessments prior to PD or death will be censored at the last valid disease assessment. Details censoring rule will be provided in the SAP.Overall survival (OS): defined as the time from the date of randomization to death from any cause. Participants without death prior to the analysis cut-off date will be censored at the last date the participant was known to be alive or the cut-off date, whichever is first. Details censoring rule will be provided in SAP.PFS2: defined as time from the date of randomization to the date of first documentation of PD (as assessed by investigator) after initiation of further anti-myeloma treatment or death from any cause, whichever happens first. Same censoring rule applies as in the PFS endpoint.Treatment-emergent adverse events (TEAEs)/serious adverse events (SAEs). Treatment-emergent adverse events (TEAEs) are defined as adverse events (AEs) that develop, worsen (according to the Investigator opinion), or become serious during the treatment period. The treatment period is defined as the time from first dose of study treatment up to 30 days after last dose of study treatment.Laboratory parameters.Injection site reactions (ISRs) – SC arm only.Adverse events and laboratory parameters will be graded using NCI CTCAE v5.0.PK concentrations.Number of successful injections with (investigational) isatuximab injector device defined as completion of administration per provided instructions for use with no use errors or technical issues, divided by the total number of injections.Incidence of participants with anti-drug antibodies (ADA) against isatuximab

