If the co-primary endpoints are significant, the key secondary endpoints will be tested by hierarchical testing in the order of VGPR or better rate, CT4W, incidence rate of IRs, and the percentage of participants who reported satisfied or very satisfied with the injection method used to administer the study medication.

VGPR or better rate per IRC will be summarized for the ITT population in the same way as for ORR endpoint. The non-inferiority test for non-unity null according to Farrington and Manning (1990) will be performed for VGPR or better rate. The non-inferiority margin is 0.6312 which was calculated as 40% retention of the observed historical clinical benefit of VGPR or better ratio 0.478 (upper bound of the 95% CI of rate ratio for Pd over CD38+ Pd as demonstrated in ICARIA-MM trial) under the logarithm scale then converting back to its original scale. If the lower bound of the 95% CI is not less than a non-inferiority margin of 0.6312, the non-inferiority of Isa-SC + Pd relative to Isa- IV + Pd on the VGPR or better rate will be concluded.

The PK endpoint of CT4W will be summarized for the PP-PK population for CT4W in the same way as for the C_{trough} at steady state endpoint. The non-inferiority of Isa- SC + Pd relative to Isa-IV + Pd on CT4W will be concluded if the lower bound of the 90% CI for the geometric mean ratio of CT4W is at least 80% (a non-inferiority margin of 80%).

Incidence rate of IRs will be compared between treatment arms on the safety population using the Fisher's exact test. The relative risk, odds ratio of ISA- SC+ Pd relative to Isa- IV + Pd with their 95% CI will be provided.

Percentage of participants who reported satisfied or very satisfied with the injection method used to administer the study medication based on the PESQ at C5D15 visit will be compared between treatment arms on the ITT population using the stratified Cochran–Mantel–Haenszel (CMH) method.

Analysis of other secondary endpoints

The median PFS per IRC assessment and probabilities of being progression free at different time points calculated using the Kaplan-Meier methods as well as corresponding 95% CI will be presented by treatment arm. The Kaplan-Meier PFS curves will also be provided. The Hazard Ratio (HR) estimated from the Cox proportional hazards model as well as its associated 95% CI will be provided too.

The analysis for PFS2, OS, DOR, and time-to-response (TTR) will be similar to that described for PFS per IRC assessment.

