4.5 DURATION OF STUDY PARTICIPATION

The participant will be considered in the study from informed consent signature until death, consent withdrawal, or the overall survival (OS) analysis cut-off date (approximately 30 months after LPI), whichever comes first.

The duration of the study for a participant will include a period for screening of up to 28 days. A cycle duration is 28 days. All AEs occurring after informed consent signature will be reported up to 30 days after last study treatment administration.

After study treatment discontinuation, participants will return to the study site 30 days after the last dose of study treatment for end of treatment (EOT) or before further anti-myeloma therapy initiation, whichever comes first ([Section 7](#)).

Related AEs and all SAEs regardless of relationship to the study treatment ongoing at the time of study treatment discontinuation will be followed during the follow-up period until resolution or stabilization. During the follow-up period, all (serious or non-serious) new AEs related to study treatment and any second primary malignancy will be collected and followed up until resolution or stabilization.

Participants who discontinue the study treatment due to PD will be followed up every 3 months (12 weeks \pm 7 days after last study treatment administration) for further anti-myeloma therapies, second primary malignancies, PFS2, and survival, until death or the final OS analysis cut-off date, whichever comes first. Participants who discontinue the study treatment prior to documentation of PD will be followed-up every 4 weeks until disease progression (even for participants who would initiate further anti-myeloma therapy without PD), and then after confirmation of disease progression, every 3 months (12 weeks) for further anti-myeloma therapies, second primary malignancies, PFS2, and survival, until death or the final OS analysis cut-off date, whichever comes first.

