7.1.1 Permanent discontinuation

Permanent treatment discontinuation is any treatment discontinuation associated with the definitive decision from the Investigator not to re-expose the participant to the study treatment at any time during the study, or from the participant not to be re-exposed to the study treatment whatever the reason. In rare instances, it may be necessary for a participant to permanently discontinue study intervention.

If one of the study treatments is prematurely permanently discontinued, then other drug(s) can be continued until disease progression or unacceptable toxicity or participant's wish to discontinue further study treatment. During this period the participant will remain in the study and continue being assessed per SoA. If all study treatments are permanently discontinued, the visit will be treated as the last dosing day with the IMPs, with subsequent relevant assessments per SoA.

In case of permanent treatment discontinuation due to disease progression, follow up will be every 3 months for further antimyeloma therapy, second primary malignancies, PFS2, and survival until death, or final OS analysis cut-off date, whichever occurs first. See the SoA for data to be collected at the time of discontinuation of study intervention and follow-up and for any further evaluations that need to be completed.

7.1.1.1 *List of criteria for permanent discontinuation*

The participants may withdraw from study treatment if they decide to do so, at any time and irrespective of the reason, or this may be the Investigator's decision. All efforts should be made to document the reason(s) for treatment discontinuation and this should be documented in the eCRF.

Isatuximab, pomalidomide, and/or dexamethasone can be discontinued permanently. The participant will remain on study treatment until the last study treatment is discontinued. The reason for permanent discontinuation will be captured in the appropriate eCRF page.

All efforts should be made to document the reason for discontinuation of treatment with the study treatment:

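### PFS2 borrows the PFS censoring rule, which censors before the further therapy after which PFS2 progressions are counted

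*Protocol*

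**What the plan says.** The endpoint tables in Protocol Section 1.1 (Synopsis) and Section 3 (Table 6) time PFS2 from randomization to investigator-assessed progression after further anti-myeloma treatment has begun, or death from any cause. Both then add: "Same censoring rule applies as in the PFS endpoint".

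The PFS rule just above places censoring at the "last valid disease assessment not showing disease progression performed prior to initiation of a further anti-myeloma treatment", or at the analysis cut-off if that comes first. It continues: "Patients with two or more consecutive missed assessments prior to PD or death will be censored at the last valid disease assessment". Only the details of PFS censoring are left to the SAP.

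Two neighbouring endpoints are worded differently. For OS: "Participants without death prior to the analysis cut-off date will be censored at the last date the participant was known to be alive"; an earlier cut-off takes precedence. For DOR, censoring is explicitly limited to participants without an event: "In the absence of PD or death before the analysis cut-off date, the DOR will be censored".

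The analysis text gives PFS2 no rule of its own: "The analysis for PFS2, OS, DOR, and time-to-response (TTR) will be similar to that described for PFS per IRC assessment". Section 9.2.3.2 says the same in substance.

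Follow-up is planned past first progression. Section 4.5 has participants seen "every 3 months (12 weeks) for further anti-myeloma therapies, second primary malignancies, PFS2, and survival", and Section 7.1.1 says that "follow up will be every 3 months for further antimyeloma therapy, second primary malignancies, PFS2, and survival until death" or the final OS cut-off. Footnote d of the Schedule of Activities (Section 1.3) also collects the date of progression on further therapy.

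**The concern.** PFS2 exists to measure what happens through the next line of therapy. The borrowed rule stops the clock before that line begins. For anyone who starts next-line therapy the order is: PFS censoring date, start of further therapy, PFS2 progression. The event the endpoint is meant to count always falls after the date at which the rule censors.

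At stake are the descriptive PFS2 results per arm: Kaplan-Meier curves, medians and landmark rates. The two ways of applying the sentence push these in opposite directions, so the reported figure would depend on an interpretation that the protocol does not settle. Under either one, part of the 12-weekly PFS2 follow-up that sites must collect would go unused.

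**Working it through.** The protocol gives no event count, power or sample size for PFS2, so there is no figure to reproduce. The check is first logical, then by example, then by illustration.

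**1. Two ways to apply the sentence**

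- *Strict:* the rule overrides later events. Everyone on next-line therapy is censored before it, so no later progression or death can count. What remains is deaths without next-line therapy.
- *Lenient:* the rule applies only to event-free participants, as the DOR wording suggests. Those who fail on next-line therapy keep their full time; those still event-free are censored back to before it. Whether observed time is kept then depends on the outcome.

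**2. Example without assumed rates**

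A and B both progress and start next-line therapy at month 6. A progresses again at month 12. B is event-free at a cut-off at month 15. With 4-weekly assessments, the last progression-free assessment is about 6 − 28/30.4 ≈ 5.1 months, that is, about month 5.

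| Rule | A | B | Kaplan-Meier step at month 12, these two only |
|---|---|---|---|
| Strict | censored, about month 5 | censored, about month 5 | no event; nobody at risk |
| Lenient | event, month 12 | censored, about month 5 | 1 at risk: 1 − 1/1 = 0 |
| PFS2-specific | event, month 12 | censored, month 15 | 2 at risk: 1 − 1/2 = 0.5 |

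Under the lenient reading B is missing from the risk set when A fails, although B was under observation and event-free.

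**3. Illustration of size**

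From the protocol: median PFS 11.53 months (Section 2.2.3.1, the earlier phase 3 trial of the IV combination), 534 participants, and cut-offs about 6 and 30 months after last patient in (Section 9.4).

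Assumed: exponential times; progression is 70% or 90% of first PFS events; 60% or 90% of progressors start next-line therapy at progression; median 5 or 10 months from there to a PFS2 event; median 6 months to death after progression without next-line therapy; uniform accrual over 12 or 24 months; dropout of 1% or 2% per month; 4-weekly assessments. These give 32 scenarios.

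Bias is the Kaplan-Meier estimate of 12-month PFS2 under the rule minus the true 12-month PFS2, in percentage points:

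| Reading | Primary cut-off | 30 months after last patient in |
|---|---|---|
| Strict | about +2 to +20 | about +3 to +20 |
| Lenient | about −2 to −5 | about −0.5 to −2 |

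A PFS2-specific rule stays within about 0.2 points of the truth at both cut-offs. The lenient bias shrinks with longer follow-up because fewer participants are still event-free on next-line therapy; the strict bias does not shrink.

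**The case against.** The strongest reply is that the sentence can be read by analogy: censor event-free participants at the last assessment not showing the progression that this endpoint counts. The planned follow-up shows that events after further therapy are meant to count, and the SAP, which is not at hand, is the natural place to say so. The intent is indeed clear. But this reading departs from the sentence as written, and the protocol fixes the rule itself, leaving only details open. A SAP that follows the sentence repeats the error; one that departs from it contradicts the protocol. The reply therefore supports the correction.

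Three limits stand.

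- The lenient-reading bias depends on the cut-off, so the primary cut-off must not be quoted alone. Secondary endpoints are promised there only where applicable.
- A reader might infer that the PFS2 median would be reported some months too short. At the primary cut-off the correctly censored median is not reached in 12 of the 32 scenarios, so no general statement about the median is supported there.
- A reader might infer that the missed-assessment clause can never fit PFS2. Sections 1.3, 4.5 and 8.2 keep participants who start further therapy without progression on 4-weekly assessments until progression, so for them the clause has a matching schedule. The misfit concerns those followed only every 12 weeks after first progression.

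**Conclusion.** The concern holds as a contradiction between the PFS2 definition and its stated censoring rule, present in both endpoint tables. It is a rule stated wrongly, not a detail left to the SAP. The contradiction needs no assumed rates. The sizes in the illustration do, since almost every input apart from the PFS median, the sample size and the cut-offs is assumed; they show direction and order of magnitude only.

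A reader might go further and infer that the comparison of arms or the trial's main conclusion is at risk. The documents do not support that. PFS2 is an other secondary endpoint outside the hierarchy in Section 9.2.5. The co-primary endpoints, the sample size and OS do not use this rule. If the two arms behave alike, the error is the same in both and the hazard ratio is not systematically shifted. Nor do the documents show that the analysis would be run wrongly. They show that the rule, followed as written, gives a wrong result. The correction should be made, but it is not critical to the trial's primary claim.

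**What to change.** In Section 1.1 and in Table 6 of Section 3, replace the borrowed-rule sentence with a PFS2 rule modelled on the OS rule:

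*Participants with neither PD after initiation of further anti-myeloma treatment nor death before the analysis cut-off will be censored at the last date known to be alive and free of a PFS2 event, or the cut-off date, whichever is first; initiation of further anti-myeloma treatment does not censor PFS2.*

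Do not carry the PFS missed-assessment clause over unchanged to participants followed only every 12 weeks after first progression.

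The cost is one sentence in two places, with the SAP aligned to it. No new data are needed, because further therapy, the progression date on it and survival are already to be collected.

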1.2 SCHEMA

Figure 1 - Graphical study design

C_{trough} = trough concentration; CT4W = C_{trough} at 4 weeks; IsaPd = Isatuximab + Pomalidomide + dexamethasone; IV = intravenous; ORR = overall response rate; PESQ = patient experience and satisfaction questionnaire; RRMM = relapsed and/or refractory multiple myeloma; SC= subcutaneous; VGPR = very good partial response

1.3 SCHEDULE OF ACTIVITIES (SOA)

Table 1 - Schedule of activities

Evaluation/ Procedure ^a	Screening/Baseline	Cycle 1 ^{ee}			Cycle 2 ^{ee}		Subsequent cycles ^{ee}		End of treatment	Follow-up ^d	Notes	
	Days -28 to -1	D1 ^c	D8	D15 ^c	D22	D1 ^c	D15 ^c	D1 ^c	D15 ^c	D30 (±5) after last study treatment administration or before the next therapy		D = Day
Informed consents ^e	X											
Training participants on ePRO technology		X										
Contraceptive counseling ^f	X											
Inclusion/exclusion criteria	X											
Randomization ^b	X											
Hepatitis B and C and HIV serologies ^g	X										As clinically indicated	
Demography, medical/surgical and disease history ^h	X											
Performance status (ECOG)	X	X				X		X		X	ECOG = Eastern Cooperative Oncology Group	
Prior/concomitant medication	Continuously throughout the study period (and within 21 days before first IMP administration)											
Isatuximab administration and administration data		X	X	X	X	X	X	X	X			
Pomalidomide ⁱ		D1 to D21			D1 to D21		D1 to D21					

Evaluation/ Procedure ^a	Screening/Baseline	Cycle 1 ^{ee}				Cycle 2 ^{ee}		Subsequent cycles ^{ee}		End of treatment	Follow-up ^d	Notes
	Days -28 to -1	D1 ^c	D8	D15 ^c	D22	D1 ^c	D15 ^c	D1 ^c	D15 ^c	D30 (±5) after last study treatment administration or before the next therapy		D = Day
Dexamethasone (before isatuximab when co-administered) ⁱ		D1, 8, 15, and 22				D1, 8, 15, and 22		D1, 8, 15, and 22				
Patient expectations Questionnaire (PEQ) ^j		X										
Patient experience and satisfaction Questionnaire (PESQ) and Patient's assessment of treatment (PAT) Questionnaire ^k			X	X	X	X	X	on D1 of Cycles 3 and 4	C5 up to EOT	X		
HRUPQ questionnaire		X	X	X	X	X				X	X	
EORTC QLQ-C30 and QLQ-MY20, EQ-5D-5L Questionnaires		X				X				X	X	
IADL and ADL questionnaires		X										
Physical examination ^l	X	X				X		X			X	
Weight (height at baseline) ^m	X	X	X	X	X	X	X	X			X	
Vital signs (HR, Temperature, RR or SPO ₂ , BP) ⁿ	X	X	X									
Hematology ^o	X	X	X	X	X	X	X	X	up to C5	X		
Serum chemistry ^p	X	X	X	X		X		X		X		

Evaluation/ Procedure ^a	Screening/Baseline	Cycle 1 ^{ee}		Cycle 2 ^{ee}		Subsequent cycles ^{ee}		End of treatment	Follow-up ^d	Notes	
		Days -28 to -1	D1 ^c	D8	D15 ^c	D22	D1 ^c	D15 ^c	D1 ^c	D15 ^c	
PT/INR, PTT	X	As clinically indicated								X	PT/INR = prothrombin time/international normalized ratio PTT = partial thromboplastin time
Urinalysis ^g	X	As clinically indicated								X	
Thyroid function tests (TSH, and free T4) ^r	X	Once a year until EOT or as clinically indicated								X	TSH = thyroid-stimulating hormone EOT = end of treatment
Antibody screening test ^s	X				X						Antibody screening test: Blood typing and complete blood phenotyping and antibody screening
Pregnancy testing [FCBP] ^t	X	X	X	X	X	X	X		X	X	FCBP = female of childbearing potential
AE/SAE reporting ^u	Continuously through the study period ^v								X (related AEs, all ongoing SAEs, second primary malignancy)	AE = adverse event SAE = serious adverse event	

Evaluation/ Procedure ^a	Screening/Baseline	Cycle 1 ^{ee}			Cycle 2 ^{ee}		Subsequent cycles ^{ee}		End of treatment	Follow-up ^d	Notes			
	Days -28 to -1	D1 ^c	D8	D15 ^c	D22	D1 ^c	D15 ^c	D1 ^c	D15 ^c	D30 (±5) after last study treatment administration or before the next therapy		D = Day		
Local tolerability at injection site after isatuximab SC administration– participant assessment using diary ^w		Continuously throughout up to Cycle 9/D1												
Local tolerability at injection site after isatuximab SC administration – investigator assessment ^x		Continuously throughout the study period up to EOT visit									EOT = end of treatment			
12 lead ECG	X	As clinically indicated						X			ECG = electrocardiogram			
Extramedullary disease (plasmacytoma) ^y	X	If present at baseline								if EOT without progressive disease	EOT = end of treatment			
Bone disease ^z	X	As clinically indicated								if EOT without progressive disease	FAMT= Further Anti-Myeloma Therapy			
Bone marrow (BM) aspiration/biopsy for determination of % of plasma cells (local data) ^{aa}	≤21 days	As clinically indicated												

Evaluation/ Procedure ^a	Screening/Baseline	Cycle 1 ^{ee}			Cycle 2 ^{ee}		Subsequent cycles ^{ee}		End of treatment	Follow-up ^d	Notes	
	Days -28 to -1	D1 ^c	D8	D15 ^c	D22	D1 ^c	D15 ^c	D1 ^c	D15 ^c	D30 (±5) after last study treatment administration or before the next therapy		D = Day
Myeloma-specific Lab tests (centralized) ^{bb}	X	X				X		X		X	If EOT without progressive disease assessment	
Bone marrow aspiration for cytogenetics assessment (central data) ^{cc}	X											
Bone marrow aspiration for MRD assessment (central data) ^{dd}	X										CR = complete response MRD = minimal residual disease VGPR = very good partial response	
Bone marrow aspiration for genomic and genetic profiling (central data)	X									At time of progression		
PK (isatuximab)												
Immunogenicity (ADA)												
Other	Follicle-stimulating hormone and estradiol (as needed in women of non childbearing potential only)											

Abbreviations: ADA = Anti-Drug Antibody; AEs = Adverse events; AESI = Adverse events of special interest; ALT = Alanine Aminotransferase; ANC = Absolute Neutrophil Count; anti-HBc = antibody to hepatitis B core antigen; anti-HBs = antibody to hepatitis B surface antigen; AP = Alkaline Phosphatase; AST = Aspartate aminotransferase; BMA = Bone marrow aspiration; BP= blood pressure; BUN = Blood urea nitrogen; C = Cycle; CBC = Complete blood count; CR = Complete response; CD38 = Cluster of differentiation 38; CT = Computed tomography; D = Day; DNA= deoxyribonucleic acid; ECOG = Eastern Cooperative Oncology Group; eCRF = electronic case report form; EORTC QLQ-c30= European Organization for Research and Treatment of Cancer Quality of Life Questionnaire; EORTC QLQ-MY20 = Quality of Life Multiple Myeloma module; EQ-5D-5L= The European Quality of Life Group Questionnaire with 5 Dimensions and 5 Levels; EOT= end-of-treatment; FAMT= Further Anti-Myeloma Therapy; FCBP = Female of childbearing potential; FPG = Fasting plasma glucose; FISH= fluorescent in Situ Hybridization; HBsAg = hepatitis B surface antigen; HBV = hepatitis B virus; HCV = hepatitis C virus; HRUPQ = healthcare resource utilization and productivity questionnaire; IAT = Indirect antiglobulin test; IFE= immunofixation; IgM = immunoglobulin M; IMWG= International Myeloma Working Group; INR = International Normalized Ratio; IR = Infusion reactions; IRT= Interactive Response Technology; ISR = Injection site reactions; IV = Intravenous; LDH= Lactate dehydrogenase; MDRD = Modification of Diet in Renal Disease; MRD = Minimal residual disease; MM = Multiple myeloma; MRI = Magnetic resonance imaging; PCR = polymerase chain reaction; PD= Progressive Disease; PAT = patient's assessment of treatment; PEQ = patient expectations questionnaire; PEQ-BL = patient

expectations questionnaire at baseline; PESQ = patient experience and satisfaction questionnaire; PET = Positron emission tomography; PK = Pharmacokinetic; PR = Partial response; PS = Performance status; PT = Prothrombin time; PTT = partial thromboplastin time; RNA = ribonucleic acid; RR = respiratory rate; sCR = stringent complete response; SC = Subcutaneous; SGOT = Serum glutamate-oxalate transferase; SGPT = Serum glutamate-pyruvate transferase; sFLC = Serum free light chain; SAE = serious adverse event; SPEP = Serum M-protein immunoelectrophoresis; TSH = Thyroid stimulating hormone; VGPR = Very good partial response; UPEP = Urine M-protein immunoelectrophoresis.

- a **Evaluation:** Assessments to be performed prior to study treatment/premedication administration unless otherwise indicated. Results should be reviewed by the Investigator.
- b **Randomization:** To take place once the consented participant has completed all the necessary screening procedures and is deemed eligible (based on assessments including myeloma specific results from central laboratory (see footnote "bb") and hematology/biochemistry local laboratory results) for randomization by the investigator or designee. All eligible participants must be randomized by contacting the Interactive Response Technology (IRT). Every effort should be made to start treatment within 3 working days of randomization.
- c **Day 1 and Day 15 (28-day cycle [± 3 day]):** Day 1 of Cycle 1 refers to the day the participants receive the first dose of study treatment administration. Day 1 of Cycle 2 corresponds to D29 of Cycle 1. Day 1 of each subsequent cycle corresponds to Day 29 (± 3 day) of the previous cycle. Day 8 and Day 22 window (± 1 day).
- d **Follow-up:** Participants who discontinue study treatment due to disease progression will be followed every 3 months (12 weeks) (± 7 days after last study treatment administration) for further antimyeloma therapy, second primary malignancies, PFS2, and survival until death, or final OS analysis cut-off date, whichever occurs first. Participants who discontinue the study treatment prior to documentation of PD will be followed up every 4 weeks until disease progression (even for participants who would initiate further antimyeloma therapy without PD), and then after confirmation of disease progression, every 3 months (12 weeks) for further anti-myeloma therapies, secondary malignancies, PFS2, and survival, until death or the final OS analysis cut-off date, whichever comes first. The information on the further antimyeloma therapy will consist of drug name, start and stop date, best overall response, and date of progressive disease.
- e **Informed consent:** Informed consent should be signed before any study-specific procedures. It can be signed more than 28 days prior to inclusion. Screening time indicates in which time frame exams used to support eligibility have to be done prior to inclusion.
- f **Contraceptive counseling:** Contraceptive counseling is to be done before initiation of each cycle prior to pomalidomide dispensing.
- g **Hepatitis B and C and HIV serologies:** Screening with serological tests for hepatitis B, and C to be done prior to randomization/enrollment (HBsAg, anti-HBs, anti-HBc [total and IgM], anti-HCV, HCV RNA level) if not performed within 1 year. Participants with anti-HBc positive (HBsAg positive participants being ineligible), HBV DNA testing by PCR will also be done at baseline. In case HBV vaccination will be started before first study treatment administration, anti-HBs should be monitored at 1, 2 and 3 months after end of vaccination. HIV serology will be tested at screening only for participants of countries where required as per local regulations.
- h **Demography:** Includes age, gender, and race. **Medical/surgical history:** Includes relevant history of previous/associated pathologies other than multiple myeloma (MM) including smoking status. **Disease history:** Includes date of initial diagnosis, stage and extent of the disease, previous MM anti-tumor therapy (type and response to), disease status at inclusion, time on treatment, and duration of response.
- i **Pomalidomide/Dexamethasone administration data:** Participants will be asked to maintain a diary to record the doses of pomalidomide/dexamethasone (except those administered by the study nurse/Investigator).
- j **Patient Expectations Questionnaire (PEQ):** Patient Expectations Questionnaire (PEQ-BL) will be completed on Cycle 1/D1 by the participant at the site prior to discussing their health/disease status, and prior to study treatment administration or other study related procedures. The time estimated to complete this questionnaire is 5 minutes (Appendix 15, [Section 10.16](#)).
- k **Patient experience and satisfaction Questionnaire (PESQ) and Patient's assessment of treatment (PAT) Questionnaire:** Patient Experience and Satisfaction Questionnaire-Follow-Up (PESQ-FU) will be completed on Cycle 1/D8, D15, D22, Cycle 2/D1, D15, Cycle 3/D1, Cycle 4/D1 and on Day 15 from Cycle 5 onwards. The overall patient experience and satisfaction questionnaire-end of treatment (PESQ-EOT) and PAT will be completed at the EOT visit by the participant at the site prior to discussing their health/disease status, or other study-related procedures. The time estimated to complete this questionnaire is 5 to 10 minutes (Appendix 15, [Section 10.16](#)).
- l **Physical examination:** To be performed at screening, prior to study treatment administration on Day 1 of Cycle 1, and then on Day 1 of each subsequent cycle (a flexibility of a maximum of 24 hours before IMP administration is allowed), and at the EOT visit. Consists of examination of major body systems including neurological, digestive, extramedullary myeloma localizations, respiratory, hepatomegaly, splenomegaly, and lymphadenopathy.
- m **Weight:** Weight will be assessed for participants in both arms on screening, at each administration of Cycle 1 and 2, at D1 of subsequent cycles, and at EOT.
- n **Vital signs:** Heart rate, temperature, respiratory rate (or pulse oximetry for at-home administration), and blood pressure to be assessed pre-administration, one hour after start of first administration and, for the IV arm only, 30 minutes after the start of the subsequent infusions. On site, vital signs are to be assessed at end of infusion/injection up to Cycle 5, and as clinically indicated. If at-home administration, vital signs are to be taken systematically just before and at the end of injection.
- o **Hematology:** Complete blood count (CBC) to be performed weekly at Cycle 1, at D1 and D15 from Cycle 2 to Cycle 5 and at D1 only from Cycle 6 onwards, and to be reviewed by the Investigator within 1 working day before the day of dosing. If Grade 4 neutropenia is observed, the assessment of neutrophil count will be done every 2 to 3 days until ANC $\geq 0.5 \times 10^9/L$ and at least weekly thereafter until ANC $\geq 1.0 \times 10^9/L$; platelet count can be assessed weekly or until $\geq 50\,000/mm^3$.

p Serum chemistry: To be performed and reviewed by the Investigator within 1 working day before the day of dosing. **Chemistry includes:** Fasting glucose, albumin, total protein, aspartate aminotransferase (AST) (serum glutamate-oxalate transferase [SGOT]), alanine aminotransferase (ALT) (serum glutamate-pyruvate transferase [SGPT]), bilirubin (total and direct), alkaline phosphatase (AP), lactate dehydrogenase (LDH), sodium, potassium, chloride, venous bicarbonate/carbon dioxide (if assessed only on arterial blood, should be done only if clinically indicated), total calcium, magnesium, phosphate, uric acid, urea/blood urea nitrogen (BUN), serum creatinine, and estimated glomerular filtration rate (MDRD equation – Appendix 2 [[Section 10.2](#)]).

q Urinalysis: Quantitative or alternatively semi-quantitative urinalysis at baseline (including red blood cells, protein, glucose, pH, ketones, bilirubin, and leukocytes) , and qualitative urinalysis (dipstick) after start of study treatment (including blood, protein, glucose, pH, ketones, bilirubin, and leukocytes).

r Thyroid function tests (Thyroid stimulating hormone [TSH], and free T4): To be performed at baseline and once a year thereafter until EOT or as clinically indicated, and at EOT. Free T3 to be done only if clinically relevant.

s Antibody screening test: Blood typing and complete blood phenotyping (C,c; E,e; Kell. Kidd; Duffy; S, s is recommended, if not available follow site's standard) if not already done, and antibody screening (indirect Coomb's test, indirect antiglobulin test [IAT]) to be obtained prior to Cycle 1/D1 study treatment administration. The IAT to be repeated at Cycle 2/D1; if the test is not performed at this visit, it can be done at the next blood sampling. Results of IAT will be recorded in the eCRF, including those performed prior to any red blood cells transfusion during study treatment. Red blood cells transfusions are to be recorded in the eCRF. During the study treatment the transfusion service should follow the recommendations issued in the AABB bulletin in case of red blood cells transfusion is needed. The web link to the AABB bulletin will be indicated on the study participant card (Appendix 13, [Section 10.14](#)). Blood type card will be kept by the participant with the study card and the blood bank needs to be informed that the participant is receiving a treatment with an anti-CD38 and a potential interference with the indirect Coombs test is possible.

t FCBP: A female of childbearing potential (FCBP) is a sexually mature woman who: 1) has achieved menarche at some time point, 2) has not undergone a hysterectomy or bilateral oophorectomy and bilateral salpingectomy; or 3) has not been naturally postmenopausal for at least 24 consecutive months. Serum or highly sensitive urine pregnancy tests for FCBP must be performed within 10 to 14 days and again within 24 hours of initiation of study treatment. Repeat pregnancy test every week for the first 4 weeks and then every 28-days while on therapy and during interruptions in therapy (or every 14 days in case of irregular menstrual cycles) and for at least 28 days after discontinuation of pomalidomide (14 and 28 days in case of irregular menstrual cycles), and monthly up to 5 months following isatuximab discontinuation, whichever occurs last. All participants must be counseled before initiation of each cycle prior to pomalidomide dispensing about pregnancy precautions, risks of fetal exposure and other risks. All participants enrolled into this study, must be registered in and must comply with all requirements of the Global Pregnancy Prevention Plan (GPPP) (if pomalidomide was provided by Sponsor) or the country specific risk management plan (if commercial pomalidomide is used).

